9.2 Background Characteristics

9.2.1 Subject Disposition

The number of subjects in the following analyses sets will be summarized:

- All Subjects Set
- Randomized
- FAS (randomized and dosed)
- Safety Set

The number and percentage of subjects in each disposition category will be summarized with the number in the FAS as the denominator, together with the number of subjects randomized but never dosed:

- Randomized but never dosed (only showing number of subjects)
- Completed treatment
- Prematurely discontinued treatment and the reasons for discontinuations
- Last completed on-treatment scheduled visit for subjects who discontinued treatment
- Completed study
- Prematurely discontinued the study and the reasons for discontinuations

A listing will be provided for subjects who discontinued treatment or who discontinued study with reasons for discontinuation. A randomization listing will be provided with subjects ordered by randomization date.

9.2.2 Demographics and Baseline Characteristics

Demographic data will be summarized based on the FAS:

- Age
- Age groups (< 18 and ≥18 years)
- Sex (female and male)
- Ethnicity

- Race

Baseline characteristics will be summarized based on the FAS:

- Weight (kg)
- Weight z-score (subjects ≤ 20 years old) Weight, adjusted for age and sex, will be analyzed as weight-for-age z-score (weight z-score). The calculation of weight z-score is similar to that of BMI z-score (using the CDC growth charts and the derivation described). Using the same equation as in the CDC growth charts and the derivation described in the website below, X in the equation is the collected weight and L , M , and S parameters are selected from the CDC weight-for-age chart. The WTAGE file contains these parameters by sex and age; it is available at the website http://www.cdc.gov/growthcharts/percentile_data_files.htm. NOTE: The CDC growth charts are designed for use in pediatric populations (2 to 20 years of age); therefore, weight z-score will be calculated only for subjects in this age range.
- Height (cm)
- Height z-score (subjects ≤ 20 years old) Height, adjusted for age and sex, will be referred to as height-for-age z-score (or height z-score). The calculation of height z-score is similar to that of BMI z-score (using the CDC growth charts and the derivation described). Using the same equation as in the CDC growth charts and the derivation described in the website below, X in the equation is the collected height and L , M , and S parameters are selected from the CDC height-for-age chart. The STATAGE file contains these parameters by sex and age; it is available at the website http://www.cdc.gov/growthcharts/percentile_data_files.htm. NOTE: The CDC growth charts are designed for use in pediatric populations (2 to 20 years of age); therefore, height z-score will be calculated only for subjects in this age range.
- BMI (kg/m^2)
- BMI z-score (subjects ≤ 20 years old)
- Percent predicted FEV₁ at screening (<70, ≥ 70)
- Percent predicted FEV₁ at baseline (<40, ≥ 40 to <70, ≥ 70 to ≤ 90 , >90)
- Percent predicted FEV₁ at baseline
- FEV₁ (L)
- FVC (L)
- Percent predicted FVC
- FEF_{25-75%} (L/sec)
- Percent predicted FEF_{25-75%}
- FEV₁/FVC
- VO₂max
- Exercise duration during CPET

- Oxygen consumption (VO_2) at anaerobic threshold (AT) (the point during exercise at which lactate starts to accumulate)
- Functional VO_2 gain
- Slope of pulmonary ventilation (VE) vs. carbon dioxide production (VCO_2)
- Cystic Fibrosis Questionnaire-Revised (CFQ-R) respiratory domain score
- Overall Patient Health Questionnaire (PHQ-8) score
- Generalized Anxiety Disorder (GAD-7) score
- Physical activity as determined by actigraphy
- Duration of sleep time during the night

- Received dornase alfa before first dose of study drug (Yes, No)
- Received any inhaled antibiotic before first dose of study drug (Yes, No)
- Received any bronchodilator before first dose of study drug (Yes, No) Note: On the Prior and Concomitant Medications page, only those coded as bronchodilator will be included.
- Received any inhaled bronchodilator before first dose of study drug (Yes, No) Note: On the Prior and Concomitant Medications page, only those coded as bronchodilator will be included.
- Received any inhaled bronchodilator before first dose of study drug (Short-Acting Only, vs (Short-Acting and Long-Acting) or Long-Acting only, vs No)
- Received any inhaled hypertonic saline before first dose of study drug (Yes, No)
- Received any inhaled corticosteroids before first dose of study drug (Yes, No)

Medical history summary will be presented for the FAS.

The important protocol deviation programming rules (based on the clinical database) are provided in Appendix G. Important protocol violations/deviations (based on the clinical database or from the site deviation log) will be summarized descriptively based on the FAS. Important protocol deviations/violations will be provided as a subject data listing.

9.2.3 Prior and Concomitant Medications

Medications used in this study will be coded by using the World Health Organization Drug Dictionary Enhanced (WHODDE) and categorized as the following:

- **Prior medication:** medication started before initial dosing of study drug, regardless of when it ended.
- **Concomitant medication:** medication continued or newly received at or after initial dosing of study drug to 28 days after the last dose of study drug.
- **Post-treatment medication:** medication continued or newly received after 28 days after the last dose of study drug.

A given medication can be classified as a prior medication, a concomitant medication, or a post-treatment medication; both prior and concomitant; both concomitant and post-treatment; or prior, concomitant, and post-treatment. If a medication has a missing or partially missing start/end date or time and it cannot be determined whether it was taken before initial dosing, concomitantly, or more than 28 days after the last dose of study drug, it will be considered as prior, concomitant, and post-treatment.

Prior medications and concomitant medications will be summarized descriptively by preferred term (PT) based on the FAS. Prior medications and concomitant medications with a frequency of $\geq 5\%$ at the PT level in any treatment group will be summarized descriptively by PT. Post-treatment medications will be listed for each subject.

In addition, to evaluate whether the medications have stable use after receiving study drug, shifts from use prior to the first dose (Yes, No) to use during the treatment-emergent period (chronic versus intermittent) will be summarized using number of subjects and percentages for the following medication categories:

- Inhaled antibiotics
- Inhaled bronchodilator
- Inhaled hypertonic saline
- Inhaled corticosteroids

A medication is considered to be used chronically during the treatment-emergent period if it is used on $\geq 25\%$ of days during the treatment-emergent period; and is considered to be used intermittently during the treatment-emergent period if it is used on $< 25\%$ of days during the treatment-emergent period. The treatment-emergent period is the period at or after the initial dosing of study drug to 28 days after the last dose of study drug.

As an intermediate step for programming purposes, medications with missing or partially missing start dates will have 2000 imputed for the missing year, January for the missing month, and 1 for the missing day; medications with missing or partially missing stop dates will have 2050 imputed for the missing year, December for the missing month, and the last day of the month for the missing day. The logic to decide the category of a medication is presented in Table 9-1:

Table 9-1 Logic for Determining the Category of a Medication

	Medication end date
Medication start date	$<$ first dose date of \geq first dose date and $>$ last dose date + 28

	study drug	\leq last dose date +28 days	days
< first dose date of study drug	P	PC	PCA
\geq first dose date and \leq last dose date + 28 days	-	C	CA
> last dose date + 28 days	-	-	A

P: Prior; C: Concomitant; A: Post

9.2.4 Study Drug Exposure

Duration of study drug exposure is defined as: last dose date – first dose date + 1 day, regardless of any interruptions in dosing. If the last dose date of study drug is missing, the subject’s discontinuation or completion date will be used for analysis purpose.

Duration of study drug exposure will be summarized descriptively as quantitative variables (number, mean, SE, SD, median, minimum [min], and maximum [max]). Additionally, the total duration of study drug exposure, defined as the sum of the subject’s duration of treatment exposure and expressed in patient years, will be provided.

Exposure summaries will be based on the FAS.

9.2.5 Study Drug Compliance

Study drug compliance will be calculated as follows:

$$100 \times [1 - (\text{Total number of days study drug interrupted}) / (\text{Duration of study drug exposure})].$$

The total number of days of study drug interrupted is defined as the sum of (number of days of study drug interrupted in each interval), where number of days of study drug interrupted in each interval is defined as the interruption end date - the corresponding interruption start date + 1.

In calculating the total number of days study drug interrupted, only interruptions with duration of ≥ 3 days will be considered. An interruption with duration of < 3 days will not be considered in the calculation.

Treatment compliance percentages will be summarized descriptively as quantitative variables (number, mean, SE, SD, median, min, and max). The n and percentage of subjects whose compliance is $< 80\%$ or $\geq 80\%$ will be summarized.

A list of subjects with $< 80\%$ compliance will be provided.

Study drug compliance will be summarized based on the FAS.

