10.10 Compliance

For study drug doses administered during study visits, doses will be administered under the direct supervision of the investigator or designee.

For study drug doses administered outside of study visits, drug accountability will be assessed at each visit by counting returned dosage units. Discrepancies will be discussed with the subject and recorded in the source documents. If a subject demonstrates continued noncompliance of study drug dosing despite educational efforts, the investigator will contact the medical monitor to discuss withdrawing the subject from the study.

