12.3.2.4 Study Drug Exposure and Compliance

Exposure to study drug (i.e., duration of treatment in days) will be defined as the last day minus the first day of study drug plus 1. Exposure will be summarized by treatment group for the Safety Set.

Dosing compliance will be calculated as the actual number of dosing occasions at which study drug was administered, as a percentage of the planned number of dosing occasions while the subject was on study drug (i.e., before study drug discontinuation or completion). Dosing compliance will be summarized for the FAS.

Duration of treatment and dosing compliance will be summarized by means of descriptive summary statistics.

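### The SAP replaces the protocol's dose-based compliance measure, without explanation, by an interruption-day measure that cannot register single missed doses and drops every gap under 3 days

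*SAP*

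**What the plan says.** Protocol 12.3.2.4 sets a dose-level definition: "Dosing compliance will be calculated as the actual number of dosing occasions at which study drug was administered", divided by the occasions planned while the subject was on study drug. Protocol 10.10 says that, for doses taken away from the clinic, "drug accountability will be assessed at each visit by counting returned dosage units". Table 3-2 schedules a study drug count at Week 12, Week 24 and the early termination visit.

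SAP 9.2.5 uses a different quantity: 100 × [1 − total interruption days / duration of exposure]. Each interruption is measured as "interruption end date - the corresponding interruption start date + 1". Short gaps are excluded: "In calculating the total number of days study drug interrupted, only interruptions with duration of" at least 3 days enter the sum. The denominator, from SAP 9.2.4, is "last dose date – first dose date + 1 day, regardless of any interruptions in dosing". The result is summarised on the FAS, split at 80%, and subjects below 80% are listed.

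SAP 9.2.5 does not mention the protocol's definition or give a reason for leaving it. SAP Section 3 lists no modifications.

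**The concern.** The two documents give the name compliance to two different quantities. The protocol counts doses. The SAP counts whole calendar days inside recorded gaps of at least 3 days, and has no term for doses taken, missed or returned. A subject with no such gap scores 100% however many single doses were missed.

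This matters because dosing is twice daily for 24 weeks and mostly at home, where scattered missed doses are a plausible form of non-adherence. Little else in the plan would show it. Pharmacokinetics is not applicable in either document, SAP Section 8 defines no per-protocol set, and the programmed deviation rules in SAP Appendix G contain no compliance rule. If VO2max shows no effect, readers will look to the compliance table when asking whether the drug was taken, and that table could show near-complete adherence whether or not it was.

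**Working it through.** Neither document states a compliance result, so there is no figure to reproduce. The check applies both formulas to the same dosing patterns.

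**Inputs**
- Two dosing occasions per day (Protocol 10.2).
- 24 weeks of treatment (Protocol 8.1), so 24 × 7 = 168 days and 168 × 2 = 336 planned occasions.
- SAP threshold: gaps under 3 days count as zero (SAP 9.2.5).
- SAP denominator: last dose date − first dose date + 1 (SAP 9.2.4).

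**Formulas**
- Protocol: 100 × occasions taken / occasions planned.
- SAP: 100 × (1 − sum of gaps of at least 3 days / duration).

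**Assumptions.** A day on which at least one dose is taken is not an interruption day. The SAP does not define the interruption end date, so two readings are shown: (A) the last day off drug, and (B) the day dosing resumes, which adds one day to every gap. On-off patterns end on their last dosing day, which shortens the span slightly. The weekly-gap row uses the repeating 7-day cycle and ignores end effects.

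| Pattern | Taken / planned | Protocol | SAP, reading A | SAP, reading B |
|---|---|---|---|---|
| One single dose missed per week | (336 − 24)/336 = 312/336 | 92.9% | 100% | 100% |
| Three single doses missed per week, other dose taken that day | (336 − 72)/336 = 264/336 | 78.6% | 100% | 100% |
| One of two doses missed every day | 168/336 | 50.0% | 100% | 100% |
| Alternate days, both doses (84 of 167 days) | 168/334 | 50.3% | 100% | 100% |
| 2-day gap every week | 5/7 | 71.4% | 100% | 1 − 3/7 = 57.1% |
| 1 day on, 2 days off (56 of 166 days, 55 gaps) | 112/332 | 33.7% | 100% | 1 − 165/166 = 0.6% |
| 1 day on, 3 days off (42 of 165 days, 41 gaps) | 84/330 | 25.5% | 1 − 123/165 = 25.5% | 1 − 164/165 = 0.6% |

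Three results follow.

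1. The first four rows score 100% on either reading. In the first three no whole day is off drug. In the fourth each gap is 1 day (2 under reading B), still below the threshold.
2. The weekly-gap and one-on/two-off rows score 100% only under reading A. Under reading B the SAP formula understates compliance for both.
3. Under reading A the formulas agree when drug is stopped for whole days in gaps of at least 3 days and both doses are taken on all other days.

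**Entry to the below-80% listing over 168 days.** The protocol formula needs at least 68 of 336 doses missed (268/336 = 79.8%), about 68/24 = 2.8 per week. The SAP formula needs at least 34 days inside gaps of 3 days or more (134/168 = 79.8%), and missed doses outside such gaps add nothing.

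**The case against.** The strongest reply is that little depends on the figure. Compliance is only summarised, split and listed. No efficacy analysis uses it as a covariate, exclusion or subgroup, and the primary model takes all FAS measurements up to Week 24, including those after treatment discontinuation (SAP 9.3.1.2). This stands. A reader might infer that the primary estimate is compromised; the documents do not support that.

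The most striking pattern, a third of the doses scoring 100%, depends on an end date the SAP does not define. This stands too. The last day off drug is the more natural reading, because it makes the + 1 give the number of days missed, but the text does not settle it. The half-dose and alternate-day patterns do not need it.

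The patterns are also extreme, and Protocol 10.10 has a check during conduct: returned units are counted, discrepancies are discussed, and continued non-compliance goes to the medical monitor. Severe non-adherence should therefore be noticed, though scheduled counts fall only at Week 12, Week 24 and early termination. That check manages subjects; it does not correct the reported figure.

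Finally, tablet counts do not prove ingestion. Protocol 12.3.2.4 does not say that occasions are to be derived from them, and the documents do not confirm that counts are in the clinical database. This stands and limits what the remedy can deliver.

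**Conclusion.** The concern holds as a discrepancy between protocol and SAP that can change reported numbers. The SAP measure scores 100% where the protocol measure scores about 50%, on either reading of the end date. If the end date is the last day off drug, it also scores 100% where the protocol measure gives 71% or about 33%. More ordinary non-adherence gives smaller gaps: 100% against 92.9% for one missed dose per week, and against 78.6% for three, the latter crossing the 80% line.

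These are properties of the formula, not predictions. How far the trial's figure will be off depends on adherence patterns that the documents do not give. If few doses are missed the two measures will be close. A reader might infer that compliance will certainly be inflated; the documents do not support that, since the error can run the other way if the end date is the resumption day.

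The primary test, alpha and power are unaffected. The compliance summary, the 80% split and the listing can overstate adherence. The point deserves correction but does not threaten the main result.

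**What to change.** In SAP 9.2.5, restore the protocol's measure: dosing occasions taken as a percentage of occasions planned while on study drug, summarised by arm with the 80% split and the listing.

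- Estimate occasions taken as (tablets dispensed − tablets returned) / 2, where counts are available in the database. Two tablets per occasion follows from the Protocol synopsis: 200 mg/125 mg tablets and a stated 400 mg/250 mg per dose, 400/200 = 2. Matching placebo is assumed to be taken in the same number.
- State how missing or incomplete counts are handled, and report how many subjects per arm have usable counts.
- Keep the interruption-day measure only as a separate line labelled as such, and define the interruption end date.
- Record the reason for any remaining departure from Protocol 12.3.2.4.

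The cost is a SAP wording change and one derivation, made before the data lock and unblinding named in SAP Section 4. First confirm that the counts are in the database and not only in source documents or accountability forms; if they are not, the cost rises. Counts may have gaps, only approximate the occasions taken and do not prove ingestion, and the reported compliance may look less favourable.

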9.3 Efficacy Analysis

Unless otherwise defined, all efficacy analyses described in this section will include all measurements up to Week 24 [inclusive], both on-treatment measurements and measurements after treatment discontinuation.

9.3.1 Analysis of Primary Efficacy Endpoint

9.3.1.1 Definition of Primary Efficacy Endpoint

The primary efficacy endpoint is the percentage change from baseline in $VO_2\text{max}$ (mL/kg/min [milliliter per kilogram per minute]) during cardiopulmonary exercise testing (CPET) at Week 24, defined as $VO_2\text{max}$ (mL/kg/min) during cardiopulmonary exercise testing (CPET) at Week 24 minus $VO_2\text{max}$ (mL/kg/min) during cardiopulmonary exercise testing (CPET) at baseline, divided by $VO_2\text{max}$ (mL/kg/min) during cardiopulmonary exercise testing (CPET) at baseline.

$VO_2\text{max}$ is the largest VO_2 value during exercise.

$VO_2\text{max}$ is found in the column(s) with a heading of VO_2 in the 20-second averaged CPET spreadsheets.

Some spreadsheets have a column reporting VO_2 in units of mL/min or L/min only, while others have an additional column reporting VO_2 as weight-based units with a designation of kg in the column header. The header title may vary, but when the term kg appears in the header, the actual units are mL/kg/min.

If the VO_2 is reported in L/min, it will need to be converted to achieve final reported units of mL/kg/min (1L=1000mL).

If there is no weight-based column showing kg (i.e., VO_2 is reported only in mL/min or L/min), the weight in kg will need to be pulled from the eCRF in order to convert these values to mL/kg/min.

9.3.1.2 Primary Analysis of Primary Efficacy Endpoint

The primary analysis for the primary efficacy endpoint will be based on a mixed model repeated measures (MMRM) using SAS PROC MIXED based on the FAS.

The model, including percentage change from baseline in $VO_2\text{max}$ (including all measurements up to Week 24 [inclusive], both on-treatment measurements and measurements after treatment discontinuation) as the dependent variable, treatment, visit, and treatment-by-visit interaction as fixed effects, with adjustment for sex (male versus female), age group at baseline (<18 versus \geq 18 years old), percent predicted FEV₁ at baseline (<70

versus ≥ 70), baseline $VO_2\text{max}$ value and subject as a random effect will be used to test the difference between active treatment group versus placebo. The primary result obtained from the model will be the treatment effect at Week 24.

Descriptive summary statistics including number of subjects, mean, standard error, and least-square means (LS means) along with the P values will be provided. In particular, the difference in LS means as well as LS means within each group and the corresponding 95% CI will be provided along with the P values to assess the treatment difference between placebo and lumacaftor in combination with ivacaftor. Additionally, the P value testing the treatment-by-visit interaction will be provided to assess the consistency of treatment effect over different visits.

The repeated-measures analysis will be based on the restricted maximum likelihood method assuming an unstructured covariance structure to model the within-subject errors. A Kenward-Roger approximation will be used for the denominator degrees of freedom. If there is a convergence problem due to the unstructured covariance matrix, a compound symmetry covariance structure will be used to model the within-subject errors. With a mixed effects model as the primary analysis model based on restricted maximum likelihood estimation and assuming that conditional on fixed and random effects, data are missing at random, no imputation of missing data will be done.

In addition, raw values of percentage change from baseline in $VO_2\text{max}$ at Week 24, and raw values of percentage change from baseline in $VO_2\text{max}$ at Week 12 will be summarized descriptively (number, mean, SE, SD, median, min, and max).

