12.1 Sample Size and Power

Assuming a common standard deviation (SD) of 10% for the primary efficacy endpoint and a dropout rate of 10%, a sample size of 33 subjects in each treatment group would provide at least 80% power to detect a difference of 7.5% between the means for the 2 treatment groups using a 2-sided test at the 0.05 significance level. If the true difference is smaller, or if there is greater variability, a larger sample size would be required to provide 80% power.

Table 12-1 shows the required sample sizes for various assumptions about the true treatment effect using a 2-sided test at the 0.05 significance level.

Because LUM/IVA has recently been approved in several countries, it is expected that additional data, independent of this study, will emerge while this study is underway and will allow more precise estimation of the true treatment effect. The final sample size will be based on these data, and the protocol may be amended as appropriate.

Table 12-1 Sample Sizes for 80% Power

True Difference Between Placebo and LUM/IVA Effects on Primary Endpoint	Sample Size Needed for 80% Power (subjects per treatment group)
5.0%	72
5.5%	59
6.0%	50
6.5%	44
7.0%	38
7.5%	33

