12.3.3 Efficacy Analysis

12.3.3.1 Analysis of Primary Variables

The primary efficacy endpoint is the percentage change from baseline in VO_{2max} during CPET at Week 24. The null hypothesis to be tested is that the mean percentage change from study baseline in VO_{2max} at Week 24 is the same for the LUM/IVA and placebo groups.

The primary analysis will use a restricted maximum likelihood (REML)-based mixed effect model for repeated measures (MMRM). The model will include the percentage change from

baseline in VO_{2max} as the dependent variable; treatment, visit, and treatment-by-visit interaction as fixed effects; and subject as a random effect with adjustment for sex (male versus female), age group at baseline (<18 versus \geq 18 years old), and ppFEV₁ at Screening (<70% versus \geq 70%). In the model, visit will be treated as a class variable, and an unstructured covariance matrix will be assumed to model the within-subject variability, which imposes no assumptions on the correlational structure. Denominator degrees of freedom for the *F*-test for fixed effects will be estimated using the Kenward-Roger approximation. No imputation of missing data will be performed.

The primary result obtained from the model will be the estimated treatment effect at Week 24 based on a contrast test. The estimated mean treatment effect at Week 24, a 95% confidence interval, and a 2-sided *P* value will be provided. Furthermore, the treatment effect at each post-baseline visit, obtained from the model, also will be provided.

If there is a convergence problem due to the use of an unstructured covariance matrix, the unstructured covariance matrix will be replaced by compound symmetry in the primary analysis.

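### The primary MMRM lists a subject random effect that duplicates the unstructured covariance, and its compound-symmetry fallback would pool the Week 24 variance with Week 12.

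*SAP*

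**What the plan says.** SAP 9.3.1.2 lists the fixed effects and covariates of the primary model and ends the list with baseline VO2max "value and subject as a random effect will be used to test the difference between active treatment group versus placebo". It then describes a REML repeated-measures analysis "assuming an unstructured covariance structure to model the within-subject errors", with Kenward-Roger denominator degrees of freedom. If the unstructured matrix causes a convergence problem, "a compound symmetry covariance structure will be used to model the within-subject errors". The missing-data sentence in the same section conditions on random as well as fixed effects.

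Protocol 12.3.3.1 has the same three elements: subject as a random effect, an unstructured matrix with Kenward-Roger, and on non-convergence "the unstructured covariance matrix will be replaced by compound symmetry in the primary analysis". Neither document drops the random effect in the fallback, and neither gives an intermediate step.

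The CPET is done on Day 1, at Weeks 12 and 24, and at early termination of treatment. SAP 9.3 limits efficacy data to Week 24, and SAP Appendix C maps post-baseline measurements up to that point to Week 12 or Week 24. The model therefore has two visits, and the primary result is the Week 24 contrast. SAP 9.3.2.2.1 and 9.3.2.2.2 reuse the model for the key secondary endpoint and most other secondary endpoints.

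**The concern.** There are two separate problems.

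**The model term.** An unstructured matrix already describes all the within-subject variance and correlation. Adding a random subject intercept puts in a variance that the data cannot separate from it. Kenward-Roger uses the information matrix of the covariance parameters, and that matrix is then singular. If a programmer codes both a RANDOM and a REPEATED statement, a convergence or Hessian problem could follow from the specification alone. It could then decide which covariance structure supplies the primary p-value.

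**The fallback.** Compound symmetry gives both visits one variance. The primary test concerns Week 24 only, so its standard error would then be built from an average of the Week 12 and Week 24 variances. Nothing in the documents supports equal variances. At stake are the type I error and the confidence interval of the primary comparison, should the fallback be used.

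**Working it through.** **The plan's own figure.** Protocol 12.1 takes an SD of 10%, 10% dropout, a difference of 7.5%, 80% power and "using a 2-sided test at the 0.05 significance level", and arrives at "a sample size of 33 subjects in each treatment group". The noncentral t distribution gives 29 evaluable subjects per arm, and 29/0.9 = 32.2, rounded up to 33. The same method reproduces all six rows of Table 12-1 (72, 59, 50, 44, 38, 33). The figure stands. It uses one SD and says nothing about Week 12.

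**Redundancy of the main model.** Let g be the random-effect variance and R the unstructured matrix. The marginal covariance at Weeks 12 and 24 is

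- V11 = g + R11
- V12 = g + R12
- V22 = g + R22

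That is 4 parameters for 3 distinct elements. The Jacobian has rank 3 of 4. Adding a constant to g and subtracting it from every element of R leaves V, and hence the likelihood, unchanged. The deficit does not depend on having two visits: there are 7 parameters with rank 6 at three visits, and 11 with rank 10 at four.

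**Redundancy of the fallback.** With compound symmetry, R11 = R22 = s + c and R12 = c. Then V11 = V22 = g + s + c and V12 = g + c: 3 parameters for 2 distinct values, rank 2 of 3. The marginal form is still compound symmetry.

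**What stays identified.** The Week 24 estimate and its model-based standard error depend on V, not on how V is split between g and R. If the software sets g to zero, both equal those from the unstructured model alone.

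**Effect of equal variances.** The documents give no by-visit SD and no Week 12 to Week 24 correlation, so the SD pairs below are assumptions. With n per arm, complete data, and SDs s12 and s24:

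- correct Week 24 SE = s24 × √(2/n)
- compound-symmetry SE = √((s12² + s24²)/2) × √(2/n)
- ratio r = √((s12² + s24²)/2) / s24
- approximate type I error = 2 × (1 − Φ(1.96 r))

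For s12 = 8, s24 = 10 and n = 30: √((64 + 100)/2) = 9.055, so r = 0.906. The SE is 2.34 instead of 10 × √(2/30) = 2.58. The approximate type I error is 7.6%.

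The simulated columns come from 40,000 null trials per setting, with 30 per arm, complete data, and correlations of 0.5 and 0.7 (0.3 as well in some settings).

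| Assumed SD Week 12, Week 24 | SE ratio r | Approx. type I | Simulated, compound symmetry | Simulated, unstructured |
|---|---|---|---|---|
| 9, 10 | 0.951 | 6.2% | 6.0–6.3% | about 5% |
| 8, 10 | 0.906 | 7.6% | 7.4–7.9% | about 5% |
| 8, 12 | 0.850 | 9.6% | 9.3–9.7% | about 5% |
| 10, 10 | 1.000 | 5.0% | 5.0–5.2% | about 5% |
| 10, 8 | 1.132 | 2.7% | 2.7–2.8% | about 5% |

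The correlation makes almost no difference. When Week 24 is the less variable visit, the loss is in power. For SDs 12 and 10, r = 1.10, and normal-approximation power at a 7.5% difference falls from 0.83 to 0.77.

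**With missing data.** REML fits were run with 33 per arm, 3 per arm missing Week 24, SDs 6 and 10, and 1,000 trials. Compound symmetry gave a mean SE of 2.07 against an empirical SD of 2.51, with 10.0% rejection. Unstructured gave a mean SE of 2.54 and 4.6%.

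**The case against.** The strongest reply is that the random-effect wording is loose language for the subject in a REPEATED statement. Both documents call the model an MMRM and assign the within-subject variability to the unstructured matrix. Coded that way, nothing goes wrong. This reading is possible. However, the SAP's missing-data sentence also conditions on random effects, and no code settles the matter.

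Second, non-convergence has not been shown. In 60 simulated datasets (33 per arm, 3 per arm missing Week 24, SDs 8 and 10, correlation 0.5), REML fits with the redundant term converged every time. The Week 24 estimate differed from unstructured alone by less than 0.0002, and the SE by less than 0.005%. Those fits were not run in PROC MIXED and had no Kenward-Roger step, so they do not rule out trouble there. They do show that a flat direction need not stop convergence.

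Third, the SAP's trigger is a convergence problem due to the unstructured matrix, and a failure caused by a redundant random term arguably does not meet it. Unstructured alone needs 3 parameters from about 66 subjects and should rarely fail.

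Fourth, a small SD difference does little harm, and its direction is unknown. All of this stands, and it limits the point to a low-cost correction.

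**Conclusion.** Both documents specify a redundant covariance term in the primary model, and a fallback that is valid for the Week 24 contrast only if the two visit variances are equal. The first holds from the text and the algebra, for any number of visits. The second has consequences only if the fallback is used and the SDs differ. Type I error is then about 6% to 9.5% in the assumed cases where Week 24 is the more variable visit, and 2.8% for SDs of 10 and 8. These sizes rest on assumed SD pairs, 30 per arm and complete data.

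A reader might infer three stronger things, and the documents support none of them:

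- That the primary effect cannot be estimated because there are only two visits. The redundancy has nothing to do with the number of visits, and the Week 24 effect stays identified.
- That the analysis will end up under compound symmetry. This is possible, not demonstrated.
- That the redundancy of the fallback makes its standard error wrong. The error comes only from the equal-variance constraint.

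**What to change.** In both documents, delete subject as a random effect. In the SAP, also remove the matching reference to random effects from the missing-data sentence. State the model as REPEATED visit / SUBJECT=subject TYPE=UN, with no RANDOM statement, and keep Kenward-Roger.

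If the unstructured fit does not converge, first try other starting values or optimiser settings. After that, use one prespecified fallback that does not pool the Week 24 variance with Week 12:

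- an ANCOVA of the Week 24 value with the same covariates, or
- compound symmetry with a sandwich variance and degrees of freedom other than Kenward-Roger.

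Heterogeneous compound symmetry is no simpler here: with two visits it has 3 parameters, as many as unstructured. Apply the same wording to the secondary MMRMs in SAP 9.3.2.2.1 and 9.3.2.2.2.

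The cost is a few words and no data. The ANCOVA would drop subjects who have only Week 12 data, but the fallback should rarely be needed. The 33 per arm is unaffected.
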